C4.4. Participant Recruitment. Recruitment will use a method already shown to be effective (see B1). Patients screening positive on the PC-PTSD screen and/or AUDIT-C, which are delivered as part of standard practice nationally in VA, will be referred by their PC or PCMH providers. Research staff will facilitate the referral process by using electronic medical record data to create monthly lists of patients screening positive and then asking their providers to refer these patients to the study. Research staff will send a letter to all referred veterans introducing the study. Study staff will then contact referred patients by phone to assess their interest in participation. Interested patients will be scheduled for a baseline research appointment within their PC clinic where study eligibility will be determined, including administering the AUDIT and PCL-5. Women will be over-sampled by devoting study resources to recruit from the Women's PC Clinics. To illustrate this recruitment method, in the Web CBT study (see B1) over a 27-month period 2,057 veterans screened positive on the AUDIT-C and/or PC-PTSD within their PC clinic. Study staff was able to contact 973 of these veterans by phone and 217 were scheduled for a baseline interview. Of the 217, 162 were determined eligible to be randomized. These numbers equate to recruiting 5 eligible participants per month. Based on the success of prior studies and our anticipated recruitment pool at Buffalo, Syracuse and Binghamton, we expect to be able to enroll 3.5 eligible participants per month. This will allow us to recruit 60 participants over 17 months.

C4.5. Assessment and Randomization. Baseline assessments will be conducted in person. Trained, VA-based research staff will obtain informed consent and HIPAA authorization. An interactive program (Qualtrax) on a laptop computer will administer the questionnaires. We have used computerized assessment in several previous studies to facilitate data collection and entry and to provide the input for the computer-generated feedback sheet used within the BMI. Following completion of the computerized self-report measures, participants will be randomly assigned to treatment condition. Urn randomization will be used to ensure a balanced distribution of key patient factors across treatment groups⁷². Included in the urn randomization: 1)

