AUDIT score ≥ 15 , 2) PCL-5 ≥ 50 , 3) gender. Demographic and severity cut-points are informed by distributional data from previous study databases. We have used these variables in previous studies with success at obtaining similar groups in each treatment condition at baseline.

Following randomization participants will complete the Clinical Administered PTSD Scale (CAPS-5). While a CAPS-5 is not needed to determine study inclusion, it will serve as the primary PTSD outcome measure because it is a more sensitive measure of PTSD severity than the PCL-5 self-report. We carefully considered whether PTSD diagnosis with the CAPS-5 should be required for study inclusion and decided that using the established cut-point on the PCL-5 provided a more ecologically valid measure for a PC-based study. A 1-hour clinical interview such as the CAPS-5 could not feasibly be used in typical PCMH practice.

A post-treatment assessment (8 weeks) and two follow-up assessments (14 weeks; 20 weeks) will be conducted following baseline (Table 5). For a brief treatment like PC-TIME, we expect the largest treatment effects (for both alcohol use and PTSD) to be at post-treatment. The purpose of follow-ups are to examine if change is maintained and to assess engagement in additional treatment. Our four assessment points will allow for a more precise trajectory of change overtime. We chose 20 weeks for our final follow-up because this is the longest interval that our study timeline would allow. Follow-ups will be in person or by phone (based on participant preference) by study staff and were designed to reduce participant burden and minimize drop-out.

C4.6. Participant Payment. Participants will be paid for time spent completing assessments at a rate of approximately \$20/ hour (baseline session- \$40, post-treatment (week 8)- \$40, 14-week follow-up- \$20, 20-week follow-up- \$20, \$20 bonus for completing all study procedures) and can earn up to \$160. Reimbursement will be by check mailed to the veteran's home. Participants will not be reimbursed for intervention sessions.

C5. Measures

C5.1. Screening Measures

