C5.4. Secondary Outcomes

Post-intervention Treatment Engagement. With HIPAA authorization, information from participants' VA administrative data will be extracted to assess if treatment condition relates to engagement in specialty mental health and substance use visits. Number of visits attended and prescriptions of psychiatric and substance use medications between enrollment and 20 week follow-up will be extracted for each participant. Drs. [name] and [name] have expertise in this type of data extraction. In addition, participants will be asked about non-VA treatment at each assessment point using the Treatment Services Review⁸⁶.

C6 Treatment Conditions

C6.1. Experimental Condition: PC-TIME. Participants randomized to the PC-TIME condition will participate in the intervention developed in the earlier study phases (see C1.2). Sessions will be conducted in-person and will be recorded for the purpose of monitoring protocol adherence.

C6.2. Control Condition: PC-TAU. PC-TAU consists of mandatory annual screens for all patients with the

AUDIT-C and PC-PTSD. Patients who score a 4 or higher on the AUDIT-C receive a Brief Advice intervention from their PC medical provider that is built into the electronic medical record as a mandatory response to a positive screen. In addition, patients who score positive on the AUDIT-C or PC-PTSD are offered a referral to the PCMHI provider within the PC clinic. PCMHI in VA consists of licensed, independent providers (typically psychologists or clinical social workers) providing brief assessment and interventions to veterans and consultation to other members of the PC team. Patients are often treated in PC for a few sessions then referred to specialty mental health and substance abuse care, if problems persist. On average, 4 PCMHI sessions are provided to PTSD patients typically focused on assessment, psycho-education, and supportive counseling ¹⁰. VA PC patients often decline referrals for alcohol use following the receipt of brief advice. There will be variability in the amount of provider contact PC-TAU participants receive, therefore we will closely measure the number and type of PC-TAU contacts and consider it as a covariate in our analyses.

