Preliminary analyses will examine distributional properties of variables and correlations among DVs. For highly collinear DVs, we will consider data reduction methods such as principal components analyses to create composite scores (this reduces the total number of tests conducted). Because we use in-person (or phone) assessments, missing data for specific questions and measures are expected to be minimal (see D3 for missing data). We will conduct multilevel growth curve modeling permitting us to estimate the between- and within-person change trajectories over time (Time: baseline, week 8 [post-tx], week 14 [F/U 1], week 20 [F/U 2]) and intervention impact (Group: PC-TIME, PC-TAU) on a given outcome variable. Time will serve as the Level 1 predictor and treatment condition on Level 2 to yield the following fixed effect equation: DV (percent of heavy drinking days or PTSD severity) = $\beta_{00} + \beta_{10}\text{Time}_{ti} + \beta_{01}\text{Treatment}_i + \beta_{11}\text{Time}_{ti} * \text{Treatment}_i + e_{ti}$. Raw data will be plotted and model fit indices will be used to determine whether change is optimally modeled linearly or

curvilinearly. Growth modeling is a powerful and flexible method well-suited for handling longitudinal data particularly in cases with missing data, nonlinear trajectories, and time-varying covariates.

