We do expect to observe a linear or curvilinear decrease in heavy drinking and PTSD severity with a significant treatment effect such that the aggregate trajectory for the PC-TIME condition will demonstrate the greatest reduction (steepest slope) of drinking behaviors and PTSD severity. We also anticipate observing a significant interaction effect where we expect no differences in the mean intercept between the groups at baseline but group differences in the mean slope or trajectory of change over time. In preliminary analyses, we will examine the equivalence of the random assignment of groups with regards to key baseline characteristics. This will involve comparison of treatment groups on sociodemographic characteristics and alcohol-related variables. In the unlikely event that groups differ significantly on any characteristics we will run analyses with indicated covariates to control for baseline differences on outcomes. Attrition effects will be evaluated by testing whether systematic differences exist between participants who complete the research and those who drop out to determine the nature of the potential bias introduced by attrition. Based on prior trials, we anticipate the level of attrition will be low (<15%) and equal across groups (see D3 for missing data). Data analysis will follow a sequence designed to answer the primary outcome question: "Does PC-TIME reduce heavy drinking and PTSD severity relative to PC-TAU?" All analyses assume two-tailed alpha = .05.

We will test the effects of PC-TIME, compared to PC-TAU, on primary variables (percentage of heavy drinking days, average number of drinks per drinking day, a dichotomous variable indicating whether one's past 30-day drinking pattern would be classified as excessive (see C5.2), PTSD severity, and drinking-related problems at post-treatment. Depending on the nature of the variable, the analyses will use either a normal distribution (e.g., for the SIP and PCL-5) or a Poisson or negative binomial model for count data (e.g., number of drinks). The intervention condition will be dummy-coded using PC-TAU as the reference group and will be included as a time-invariant covariate on Level 2 of the multilevel growth model ⁹⁴. If any covariates are identified as necessary during preliminary analyses, these will also be included in the model.

D3. Missing Data

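### Covariates are left to baseline significance tests or later judgement, while the between-group effect sizes carry no planned baseline or urn-factor adjustment

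*Combined protocol and SAP*

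**What the plan says.** The core efficacy model in D1 is a growth model: "Time will serve as the Level 1 predictor and treatment condition on Level 2 to yield the following fixed effect equation". The equation contains time, treatment and their product, with baseline as one of four time points. It has no covariates.

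Three routes can add covariates later:

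- D1 plans a preliminary "comparison of treatment groups on sociodemographic characteristics and alcohol-related variables", and then: "In the unlikely event that groups differ significantly on any characteristics we will run analyses with indicated covariates". Two classes of variable are named. There is no list and no number of tests.
- D1 adds: "If any covariates are identified as necessary during preliminary analyses, these will also be included in the model". No criterion for necessity is given.
- C6.2 notes that provider contact will vary among PC-TAU participants, "therefore we will closely measure the number and type of PC-TAU contacts and consider it as a covariate in our analyses".

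On allocation, C4.5 says: "Urn randomization will be used to ensure a balanced distribution of key patient factors across treatment groups". The factors are 1) "AUDIT score ≥ 15 , 2) PCL-5 ≥ 50 , 3) gender". No analysis is required to include them.

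Separately, the opening text of the SAP plans between-group effect sizes (Cohen's d or h) with 95% confidence intervals at each assessment, as one source for sizing a later trial. It mentions no baseline or urn adjustment for these.

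**The concern.** A covariate earns its place by predicting the outcome, and that can be judged before any data are seen. A significance test between randomized arms measures something else. With sound randomization, every significant difference is a chance event and says nothing about prognosis. The rule also runs against the design: the urn factors were chosen as key patient factors, and balancing them makes them the variables least likely to be selected.

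Contacts raise a different problem. Contact received as a trial participant comes after assignment and may depend on it. C5.4 itself treats later specialty visits as an outcome that may relate to condition. Conditioning on such a variable can move the treatment estimate away from the intention-to-treat effect. If contacts are counted only in the PC-TAU arm, the covariate is not even defined in a two-arm model.

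At stake are the effect sizes and intervals carried forward to the next trial, and whether the analysis is fixed before the data are seen.

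**Working it through.** **Sample.** C4.2: 60 × 0.85 = 51 retained, which reproduces the plan's figure. With 1:1 allocation (assumed; the ratio is not stated) that is 25.5 per arm. D1 sets two-tailed alpha at .05.

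**How often the significance rule fires.** For k independent tests the chance of at least one significant result is 1 − 0.95^k. The documents do not give k, so a range is shown.

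| Assumption | k = 5 | k = 10 | k = 15 |
|---|---|---|---|
| Independent tests, none urn-balanced (upper end) | 23% | 40% | 54% |
| Inter-test correlation 0.5 (simulated) | 18% | 29% | 36% |
| Three tests urn-balanced at an assumed 1% each: 1 − 0.95^(k−3) × 0.99³ | 12% | 32% | 48% |

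Once about ten characteristics are compared, the event is hardly unlikely.

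**What the rule selects.** In simulated urn allocation (N = 60, two prevalence sets by three urn settings, 1,500 runs each), a given urn factor was significant in 0.2 to 1.6% of trials and a non-urn factor in 5.1 to 5.7%. In a second simulation (n = 51, 4,000 runs per scenario), at least one of the three urn factors was significant in about 1% of trials, against 14% when allocation was not balanced on them.

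**Single-visit effect size, continuous outcome.** The unadjusted 95% half-width for d is about 1.96 × √(4/51) = 0.55. Adjusting for a baseline value with correlation rho multiplies the variance by 1 − rho², so the half-width is multiplied by √(1 − rho²). The documents give no rho.

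| Assumed rho | Variance factor | Half-width |
|---|---|---|
| 0.3 | 0.91 | 0.52 |
| 0.5 | 0.75 | 0.48 |
| 0.7 | 0.51 | 0.39 |

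The factor does not depend on the ratio of baseline to follow-up SD. It does not carry over directly to count or dichotomous outcomes.

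**Single-visit test and the urn factors.** The second simulation also compared models at one visit, with urn factors assumed to explain 10/30/50% of outcome variance. Under a true null, the rejection rate was 4.2/3.5/2.4% unadjusted, 4.3/3.1/2.1% with test-then-adjust, and 5.0/5.0/4.8% with the urn factors always included. Ignoring them is conservative.

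**Growth model.** A covariate that is constant over time, entered as a main effect, shifts the intercept and not the within-person change. In one simulated complete four-visit dataset (n = 60), the time-by-treatment estimate was −0.314 (SE 0.176) with and without it.

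**Contacts.** Suppose treatment has no effect, contacts differ between arms by a shift (in SD), and they correlate with outcome within arm through a shared cause. Adjustment then moves the estimate by shift × correlation. With assumed shifts of 0.5 to 1.0 and correlations of 0.1 to 0.25, this runs from 0.5 × 0.1 = 0.05 to 1.0 × 0.25 = 0.25 SD. The documents support neither range.

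**Dichotomous outcome.** With 51 observed and 20 to 50% in the smaller class, that class holds about 10 to 26 people. Treatment, baseline and three urn factors (5 coefficients) leave 2.0 to 5.1 people per coefficient. With one urn factor (3 coefficients) it is 3.4 to 8.5.

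**The case against.** The strongest reply is that little here harms the main test. Feasibility is the stated primary goal, the effect sizes are only one source for later sizing, and the growth model already uses baseline as a time point. All of that stands. It lowers the weight of the point but does not remove it: the SAP opening still commits to separate effect sizes at each visit, and those have no planned adjustment.

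A reader might infer that the significance rule biases the result or inflates type I error. The documents and the simulations do not support this: test-then-adjust rejected no more than 4.3% of true nulls. Rejection rose to 6.0 to 6.6% only when the smallest p-value of three models was taken, which the plan does not propose.

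A reader might also infer that the growth model is faulty because it estimates a baseline group difference although "we expect no differences in the mean intercept between the groups at baseline". That model is valid and unbiased. Constraining the baseline means to be equal is an optional efficiency choice whose gain could be near zero if eligibility narrows the baseline spread. It is not part of the error. Nor could four-visit gains apply to CAPS-5, which C5.2 schedules only at baseline and post-treatment.

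Finally, C6.2 says only that contacts will be considered. It does not tie them to the primary comparison, and a secondary or within-arm use is an equally open reading. The bias is therefore a risk the wording permits, not a planned defect.

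**Conclusion.** The point holds in a limited form and should be corrected. The plan states a covariate rule that does not find prognostic variables and almost never picks the factors used in allocation. It leaves a second trigger without a criterion, and it keeps open adjustment for a variable that arises after randomization.

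The demonstrable gain is twofold: a model fixed in advance, and narrower intervals for single-visit differences on continuous outcomes. At the assumed correlations, the half-width falls from 0.55 to between 0.52 and 0.39. Range restriction from the AUDIT and PCL-5 entry criteria would lower the correlation, so the gain may sit at the small end. For the D1 slope test, urn main effects change almost nothing; the case for including them there is prespecification and matching the analysis to the design.

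The size of any bias from adjusting for contacts cannot be known from the documents. The 0.05 to 0.25 SD range rests wholly on assumed inputs.

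**What to change.** 1. Delete both covariate triggers in D1 and report baseline characteristics descriptively.
2. For continuous outcomes, estimate the week 8, 14 and 20 between-group differences by ANCOVA on the pre-randomization baseline value, with the three urn factors as main effects. Standardize d by the unadjusted SD. Leave the baseline contrast unadjusted.
3. Keep the D1 growth model as planned, adding the urn factors as prespecified main effects only.
4. For count and dichotomous outcomes, prespecify the baseline value and one urn factor, named now. State that an adjusted odds ratio is conditional.
5. For CAPS-5, whose baseline interview follows randomization (C4.5), either complete the interview before randomization or prespecify the pre-randomization PCL-5 as the covariate. This applies at week 8 only.
6. Confirm that the TLFB precedes randomization; the documents do not place it.
7. Do not adjust the primary comparison for PC-TAU contacts. Describe them by arm, or use them only in a labelled secondary analysis.

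**Cost.** Mostly SAP wording, using data already collected. The ANCOVA spends four further coefficients: residual degrees of freedom fall from 51 − 2 = 49 to 51 − 6 = 45. Moving the CAPS-5 changes the visit order. The PCL-5 alternative has a limit. With equal SDs, it beats a CAPS-5 change contrast only if its squared correlation r² with week-8 CAPS-5 exceeds 2 × rho − 1, where rho is the CAPS-5 correlation between baseline and week 8. At rho = 0.7 that needs r above √0.4 = 0.63; at rho = 0.5 any non-zero correlation suffices.
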